11.6.3 Overall Survival (OS)

Overall survival (OS) is defined as the time from first dose of study drug to the date of death due to any cause. OS (in months) is calculated as $(\text{date of death} - \text{date of first dose of study drug} + 1)/30.4375$.

OS will be summarized descriptively using the Kaplan-Meier estimate. The median, 25th percentile, and 75th percentile of OS and their two-sided 95% CI (Brookmeyer & Crowley, 1982) will be calculated where appropriate. In addition, minimum and maximum will also be displayed. Kaplan-Meier plots will be provided.

The 1-year OS rate (proportion and 95% CI) will be analyzed using Kaplan-Meier methodology (Greenwood's formula, (Kalbfleisch & Prentice, 1980)).

Analysis will be performed on the FAS.

Censoring Rules

For patients who are continuing study at the time of analysis, lost to follow-up or who withdraw consent, the OS endpoint will be censored on the last date that patients were known to be alive. The date last known to be alive is derived from the CRF and may include the latest visit date for patients ongoing in the study or the latest Date of Contact on the Long-Term Follow-Up/Survival Status page, whichever occurs latest. For patients with no follow-up after first dose of study drug, OS will be censored at the date of first dose (Day 1).

11.6.4 Extent of Follow-up

The extent of follow-up is defined as the time from the date of the first dose to the last known date that the patient was alive (for patients who are alive) or death date (for patients who died).

The median extent of follow-up with 95% CI will be calculated and presented using a reverse KM approach. Analysis will be performed on the FAS.

11.6.5 Progression-Free Survival (PFS)

Progression-free survival (PFS) is defined as the time from the first dose of study drug to the date of PD or death due to any cause, whichever occurs first in the absence of documented PD. PFS (in months) will be calculated as $(\text{first event date} - \text{first dose date} + 1)/30.4375$.

PFS will be summarized descriptively using the Kaplan-Meier estimate. The median, 25th percentile, and 75th percentile of PFS and their two-sided 95% CI (Brookmeyer & Crowley, 1982) will be calculated where appropriate. In addition, minimum and maximum will also be displayed. Kaplan-Meier plots will be provided for PFS.

Analysis will be performed on the FAS.

Censoring Rules for DoR and PFS

The following censoring rules will apply to event dates for time-to-event endpoints that are based on radiographic evaluations, i.e., DOR and PFS:

- Endpoints will be censored on the date of first dose (or randomization) with duration of 1 day under the following scenarios, unless patients die within 2 consecutive tumor assessments of first dose (on or prior to week 16, i.e. Cycle 5 Day 1 plus the 10 day window, which is Study Day 122 for Cohorts 1-8 or Day 136 for Cohort 9), in which case they will be assessed as having an event on the date of death (apply to PFS only):
 - baseline disease assessment inadequate to apply RECIST1.1;
 - no disease assessments are performed during study treatment; or
 - all disease assessments performed during study treatment result in the conclusion of NE.
- Endpoints will be censored on the date of the last evaluable disease assessment prior to the start of subsequent anti-cancer therapy under the following scenarios (apply to PFS and DOR). Last evaluable assessment date is defined as the last response assessment date on or after treatment start date with a response of CR, PR, or SD.
 - PD or death occur after ≥ 2 consecutive tumor assessments (i.e., ≥ 122 days of last evaluable tumor assessment for Cohorts 1-8 or ≥ 136 days for Cohort 9) that are missed or result in the conclusion of NE;
 - patient administered subsequent anti-cancer treatment prior to documented PD or death;
 - patient lost to follow-up;
 - patient withdrawal of consent for follow-up; or
 - patients alive and without PD at the time of analysis

Date of death will be considered an event for DOR and PFS only if death occurred in the absence of receiving subsequent anti-cancer therapy, and under one of the following scenarios:

- death occurs prior to PD and < 122 days for Cohorts 1-8 or < 136 days for Cohort 9 after the first dose of study treatment; or
- death occurs < 122 days for Cohorts 1-8 or < 136 days for Cohort 9 after the last evaluable disease assessment

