- 8 Pharmacokinetic Samples: Blood samples to be collected following ECGs and assessment of vital signs as scheduled in Table 2.
- 9 Blood samples for ctDNA analysis: Blood will be collected in two 10 mL Streck brand Cell-Free DNA Blood Collection tubes allowing shipping and stability at ambient temperatures.
- 10 12-Lead ECGs: Triplicate ECGs will accompany PK sampling as described in Table 2. In addition, ECGs are to be performed as clinically indicated. Assessments will include an evaluation of heart rate, QT, and QTc intervals. RR interval should be recorded during each ECG assessment in order to calculate QTcF.
- 11 Disease Evaluations: To be performed at screening (28-day window allowed) and every 8 weeks from Cycle 1 Day 1 (\pm 10-day window for all other assessments except screening) until week 49 (~12 months) and then every 16 weeks. All on-study disease evaluations should be based on a calendar beginning from the first day of dosing. At screening/baseline, assessments are to include CT with contrast of the chest, CT or MRI of the abdomen and pelvis, as well as brain Magnetic Resonance Imaging (MRI) with and without gadolinium or CT with contrast, a whole-body bone scan (or PET or PET/CT if local standard for clinical trials) and evaluation of any superficial lesions. Subsequent disease assessments should include all sites of disease identified at baseline or suspected to have developed; bone scans may be performed half as often (every 16 weeks) as other radiology evaluations and should be performed during assessment for confirmation of disease response. More detailed guidance on exceptional circumstances is provided in the protocol. Patients who discontinued the study for reasons other than objective disease progression will continue to have disease assessments at the same frequency until patient has radiologically confirmed progression, initiates a new anticancer therapy, or death.
- 12 Adverse Events: Serious Adverse Events (SAEs) will be reported from the time of informed consent until at least 28 days after the last administration of a study treatment. Adverse events will be reported from the first day of study treatment until at least 28 days after last dose of study drug, and until resolution or stabilization of acute adverse events and/or ongoing SAEs.

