- 11 Disease Evaluations: To be performed at screening (28-day window allowed) and every 9 weeks from Cycle 1 Day 1 (± 10 -day window for all other assessments except screening) until week 49 (~12 months) and then every 18 weeks. All on-study disease evaluations should be based on a calendar beginning from the first day of dosing. At screening/baseline, assessments are to include CT with contrast of the chest, CT or MRI of the abdomen and pelvis, as well as brain Magnetic Resonance Imaging (MRI) with and without gadolinium or CT with contrast, a whole-body bone scan (or PET or PET/CT if local standard for clinical trials) and evaluation of any superficial lesions. Subsequent disease assessments should include all sites of disease identified at baseline or suspected to have developed; bone scans may be performed half as often (every 18 weeks) as other radiology evaluations and should be performed during assessment for confirmation of disease response. More detailed guidance on exceptional circumstances is provided in the protocol. Patients who discontinued the study for reasons other than objective disease progression will continue to have disease assessments at the same frequency until patient has radiologically confirmed progression, initiates a new anticancer therapy, or death.
- 12 Adverse Events: Serious Adverse Events (SAEs) will be reported from the time of informed consent until at least 28 days after the last administration of a study treatment. Adverse events will be reported from the first day of study treatment until at least 28 days after last dose of study drug, and until resolution or stabilization of acute adverse events and/or ongoing SAEs.
- 13 Long Term Follow-up: Survival status and subsequent therapies will be collected during long term follow-up every 2 months (± 14 days) from the End of Treatment Visit until death or lost to follow-up. Follow-up may be performed by telephone contact or email.
- 14 End of Treatment: Perform within 7-14 days of decision to permanently discontinue all study treatment. Assessments that have been completed in the previous 4 weeks do not need to be repeated (8 or 16 weeks for tumor assessments in accordance with schedule).

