11.6 Efficacy Analyses and Efficacy Variables

11.6.1 Objective Response Rate (ORR)

Disease assessments involving radiographic evaluations may be performed over the course of a few days. The date of response (Complete Response, CR; Partial Response, PR; Stable Disease, SD; or Not Evaluable, NE) will be recorded as the date of the last radiographic evaluation included in the series for that time point assessment. The date of progression (PD) will be recorded as the date of the first radiographic evaluation included in the series for that time point assessment to identify progression.

ORR will be categorized in accordance with RECIST v1.1. (Appendix 3) Objective Response Rate (ORR) is defined as the percent of patients documented to have a confirmed CR or PR as defined in Table 9.

Descriptive statistics (frequency and percentage) for ORR, CR, and PR will be presented. The 95% exact Clopper-Pearson CI of these response rates will be calculated. An exact test for single proportion (two-sided $\alpha = 5\%$) will be performed to test $H_0: ORR \leq 5\%$ against $H_1: ORR > 5\%$.

Best overall response (BOR) is defined as the best response among all overall responses (in the order CR, PR, SD, PD, and indeterminate NE) recorded from the start of study drug until disease progression/recurrence, or start of anti-cancer therapy, whichever comes first.

The status of best response of CR or PR must be confirmed by repeat tumor assessment within no less than 4 weeks according to RECIST version 1.1. If the status of CR or PR cannot be confirmed by repeat tumor assessment, the BOR of unconfirmed CR and PR will be determined per RECIST 1.1. The status of BOR of SD requires an on-study assessment after at least 42 days on treatment. Patients without a valid clinical response assessment will be assigned a best overall response of NE. No response will be counted after PD.

Table 9 lists out the different scenarios of confirmed response based on subsequent assessment. The status of SD requires an on-study assessment at least 42 days on study. Patients without a valid clinical response assessment will be assigned a best overall response of NE.

Table 9 Confirmed Response Based on Subsequent Assessments*

First Time Point Response**	Second Time Point Response	Confirmed Response (Best Response)*
PD	No further evaluation	PD
NE	PD	PD
CR	PD	SD or PD (1)
PR	PD	SD or PD (1)
SD	PD	SD or PD (1)
CR	CR	CR
CR	NE **	SD or NE (2)
PR	CR	PR
PR	PR	PR
PR	SD (3)**	SD
PR	NE **	SD or NE (2)

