SD	CR	SD
SD	PR	SD
SD	SD	SD
SD	NE	SD or NE (2)
First Time Point Response**	Second Time Point Response	Confirmed Response (Best Response)*
NE	CR	SD
NE	PR	SD
NE	SD	SD
NE	NE	NE

* A Best Response of SD can only be made after the patient is on-study for a minimum of six (6) weeks (42 days). If the patient is on-study less than six (6) weeks (42 days), any tumor assessment indicating stable disease before this time period will have a Best Response of NE unless PD is identified.

** Subsequent documentation of CR may provide confirmation of a previously identified CR for patients where the second integrated response was NE. Subsequent documentation of PR may provide confirmation of a previously identified PR for patients where the second integrated response was NE or SD. If the third Time Point Response (TPR) confirms the CR (or PR) then the Confirmed Response will be CR (or PR). For this study, only one (1) intervening NE is allowed between CRs/PRs. For example: CR NE CR = CR; PR NE PR = PR. Additionally, one (1) SD is allowed between PRs (e.g., PR SD PR = PR).

(1) Best response will be SD if the first TPR is after at least six (6) weeks (42 days) on-treatment. Otherwise, the best response will be PD.

- (2) Best response will be SD if the first TPR is after six (6) weeks (42 days) on-study. Otherwise, the best response will be NE.
- (3) TPR is SD if the increase from the first to the second assessment does not qualify for PD.

For patients with unconfirmed CR/PR and who subsequently drop off the study, the best overall response will be SD.

Descriptive statistics (frequency, percentage) for best overall response (CR, PR, SD, PD, NE) based on response assessments by the investigator will be presented.

The primary analysis will be conducted in the Full Analysis Population and supportive analysis will be presented in the Clinical Activity Evaluable population.

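### SAP 11.6.5 triggers Day-1 PFS censoring on scans done during treatment only, so a required off-treatment scan can be ignored

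*SAP*

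**What the plan says.** The first censoring bullet in SAP 11.6.5 puts PFS at the date of first dose, duration 1 day, in three situations. Two of them depend on treatment status: "no disease assessments are performed during study treatment" and "all disease assessments performed during study treatment result in the conclusion of NE". The exception is death within two assessment intervals of first dose, given as Study Day 122 for Cohorts 1-8 and Day 136 for Cohort 9. There is no exception for an evaluable scan after treatment stops.

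Other parts of the SAP do not stop counting scans at the end of treatment:

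- The PFS definition in 11.6.5 counts progression or death from first dose and does not restrict progression to the treatment period.
- The last evaluable assessment, used by the second censoring bullet, is "the last response assessment date on or after treatment start date with a response of CR, PR, or SD".
- Death can count as an event if "death occurs < 122 days for Cohorts 1-8 or < 136 days for Cohort 9 after the last evaluable disease assessment", with no condition that the scan was on treatment.
- Best overall response in 11.6.1 uses assessments "recorded from the start of study drug until disease progression/recurrence, or start of anti-cancer therapy, whichever comes first".

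Off-treatment scans are planned. Under SAP Table 1, footnote 11, patients who stop for a reason other than objective progression "will continue to have disease assessments at the same frequency until patient has radiologically confirmed progression", new therapy or death. Table 3, footnote 11, says the same for Cohort 9, where scans are "every 9 weeks from Cycle 1 Day 1" rather than every 8 weeks.

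**The concern.** A patient who stops every study drug before the first evaluable scan, for a reason other than progression, can still have an evaluable scan on schedule before starting any new therapy. The literal first bullet sets that scan aside. A documented progression then disappears from PFS because of when drug was stopped, and censoring that depends on stopping treatment may be informative. In another case the SAP gives two censoring dates for one patient. 11.6.5 states neither which bullet takes precedence nor what *during study treatment* means for efficacy, so two programmers could produce different PFS datasets from the same plan.

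**Working it through.** **Plan's own figures.** The window is two scan intervals plus the 10-day allowance: 2 × 8 × 7 + 10 = 122 days for Cohorts 1-8 and 2 × 9 × 7 + 10 = 136 days for Cohort 9. Both reproduce, as days elapsed from first dose.

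**When the first scan falls.** With first dose as Day 1, Week 8 is 8 × 7 + 1 = Day 57 (window Day 47-67). In Cohort 9, Week 9 is 9 × 7 + 1 = Day 64 (window Day 54-74).

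**Three patients, Cohorts 1-8.** Each has a last dose on Day 20, no on-treatment scan, a first scan on Day 57 and no new therapy. PFS in months is study day / 30.4375, so Day 1 = 0.03, Day 57 = 1.87 and Day 150 = 4.93.

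| Patient | Literal first bullet | Other 11.6.5 text |
|---|---|---|
| A: progression Day 57, death Day 200 | censored at 0.03 | PFS definition: event at 1.87 |
| B: stable Day 57, then lost to follow-up | censored at 0.03 | second bullet: censored at 1.87 |
| C: stable Day 57, death Day 150 | censored at 0.03 | death 150 − 57 = 93 days after the scan, under 122: may be an event at 4.93 |

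A patient with no scan who dies on Day 100 is an event at 100 / 30.4375 = 3.29 months on either reading, so early deaths raise no problem.

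**Does the safety definition settle it?** SAP 11.7 defines on-treatment as up to last dose + 28 days, for safety summaries. If it were borrowed, a Day 57 scan would count only with a last dose on or after 57 − 28 = Day 29, and a Day 64 scan in Cohort 9 only on or after 64 − 28 = Day 36. The Day 20 patients would still be censored at Day 1.

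**Size, on assumptions that are not in the documents.** Let f be the affected share. Other patients have exponential PFS with median 4 months, so λ = ln 2 / 4 = 0.1733 per month. All affected patients progress at Day 57 (s = 1.873 months), and median time from progression to death is 4 months. Let L = 122 / 30.4375 = 4.008 months.

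- Counting the off-treatment progressions, the median solves (1 − f)·exp(−λt) = 0.5, so t = ln(2(1 − f)) / λ.
- Under the literal rule, affected patients who die by L are events at death and the rest are censored at Day 1. The probability of death by time t (t > s) is P(t) = 1 − exp(−λ(t − s)), and P(L) = 0.309. Up to L, S(t) = [(1 − f)·exp(−λt) + f·(P(L) − P(t))] / [(1 − f) + f·P(L)].

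| f | Progressions counted | Literal rule | Error |
|---|---|---|---|
| 5% | 3.70 months | 3.91 months | +5.7% |
| 15% | 3.06 months | 3.75 months | +23% |

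The sign can reverse. Suppose affected patients have the same exponential PFS as the others, their first PFS event is always progression, and the median from progression to death is again 4 months. The true median is then 4.00 months and the literal rule gives 3.96 (−1.1%) at f = 5% and 3.86 (−3.4%) at f = 15%. The literal rule keeps their early deaths and discards the rest of their follow-up.

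For scale, with 40 patients and a true median of 4 months, 95% of uncensored sample medians fall between roughly 2.4 and 6 months.

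**The case against.** The strongest reply is that the limit is only loose wording. The SAP's version 3.0 change history describes this as the rule for patients who lack a disease evaluation after first study treatment, and Protocol 9.4.4 frames it the same way. The SAP is also careless with such terms: note (1) to Table 9 says "Best response will be SD if the first TPR is after at least six (6) weeks (42 days) on-treatment", while note (2) says on-study for the same 42-day requirement. This carries weight, and it is why the limit is best seen as unintended. It does not change the rule that would be programmed, because the change history does not override the rule text.

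A reader might infer more than the documents support:

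- *That the best-overall-response window contradicts the rule.* Best response is a different endpoint. A best response of progression beside a censored PFS is odd, but it is not two PFS answers.
- *That the death rule contradicts it.* The SAP says death is an event only if a listed scenario holds. That is a necessary condition and does not require every such death to be counted. Patient C's outcome is unclear, not strictly contradictory.
- *That departing from the protocol is itself the error.* Protocol Section 9 lets the SAP modify the protocol's plans, and PFS is not the primary endpoint. The protocol wording serves only as evidence of intent.
- *That PFS will be overstated.* The direction depends on how the affected patients fare.

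It is also fair to say that few patients can qualify. Protocol 5.1.3 allows one drug to continue when another stops. Patients who start new therapy before any evaluable scan, or who never have one, are treated alike on either reading.

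**Conclusion.** The point holds as a minor drafting defect in an operative rule. On the literal text, an on-schedule off-treatment progression is dropped from PFS, contrary to the PFS definition. Off-treatment stable disease followed by loss to follow-up has two censoring dates and no stated precedence. A death within 122 or 136 days of an off-treatment stable scan, but after Study Day 122 or 136, is left unclear.

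The documents give no count of affected patients, so neither the size nor the direction of any error in median PFS can be fixed from them. The errors of about +6% and +23% rest on an assumed 4-month median in the other patients, progression at Day 57 in every affected patient and a 4-month median from progression to death. They are illustrations, not estimates. PFS is a secondary endpoint summarized descriptively, and ORR and enrollment decisions are untouched.

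**What to change.** In both sub-bullets of the first censoring bullet in SAP 11.6.5, replace *during study treatment* with *after first dose of study treatment and before any subsequent anti-cancer therapy*.

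That edit alone leaves a gap. Take a patient whose first post-baseline scan, after two missed assessments, shows progression on Day 170. The reworded first bullet no longer applies. The second bullet sends the patient to the last evaluable assessment, which must be CR, PR or SD, and there is none. So add a sentence: if progression or death follows two or more missed or non-evaluable assessments and there is no earlier CR, PR or SD assessment, PFS is censored at Day 1, keeping the existing early-death exception. This also closes the same gap for patients still on treatment.

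With both changes patient A is an event at 1.87 months, patient B is censored at 1.87 months and patient C is an event at 4.93 months. The cost is a wording change to two sub-bullets and one added sentence, with matching programming. No new data are needed, because the off-treatment scans are already required.

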9.4.4 Progression-Free Survival

Progression-free survival (PFS) is defined as the time from date of first study treatment to first PD or death due to any cause in the absence of documented PD. Censoring for the PFS endpoint will be assigned on the date of the last tumor assessment if no assessment of tumor progression is identified and the patient does not die while on study. For patients in whom two or more sequential assessments are missed, followed by the finding of tumor progression, the PFS endpoint will be censored on the date of the last tumor assessment before the gap. Patients lacking an evaluation of disease after first study treatment will have their PFS time censored on the date of first dose with duration of 1 day. Patients who start a new anti-cancer therapy prior to documented PD will have the endpoint censored at the date of the last tumor assessment prior to the start of the new therapy. The Kaplan-Meier method will be used to obtain the estimate of median progression-free survival time.

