11.6.2 Duration of Response (DOR)

Duration of response (DOR) in months is defined as the time from date of the first documentation of confirmed objective response (CR or PR) to the first documentation of objective PD or to death due to any cause in the absence of documented PD (i.e., $\min[\text{PD date, death date}] - \text{date of the first observation of response} + 1$)/30.4375. Duration of response will only be calculated for the subgroup of patients achieving a confirmed CR or PR.

DOR will be summarized descriptively using the Kaplan-Meier estimate. The median, 25th percentile, and 75th percentile of DOR and their two-sided 95% CI (Brookmeyer & Crowley, 1982) will be calculated where appropriate. In addition, minimum and maximum will also be displayed. Kaplan-Meier plots will be provided for DOR.

DOR will be based on response assessments by Investigator. DOR will be conducted in the CAE population who have confirmed CR or PR.

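### The fixed 122/136-day gap in the PFS and DOR censoring rules equals two missed scans only until about week 49; afterwards it discards progressions and deaths after one missed scan

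*SAP*

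**What the plan says.** SAP 11.6.5 (Censoring Rules for DoR and PFS) sets one rule for both endpoints. Progression or death after at least two consecutive missed or non-evaluable assessments is censored at the last evaluable assessment. An i.e. then turns the scan count into elapsed time: at least 122 "days of last evaluable tumor assessment for Cohorts 1-8 or" at least 136 days for Cohort 9. The source of the number appears in the preceding bullet on early deaths: "on or prior to week 16, i.e. Cycle 5 Day 1 plus the 10 day window, which is Study Day 122".

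The same section says when a death is an event. Apart from deaths soon after first dose, it must fall fewer than 122 days (Cohorts 1-8) or fewer than "136 days for Cohort 9 after the last evaluable disease assessment". No count of missed scans appears there.

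The scan calendar is in footnote 11 of SAP Table 1 (Cohorts 1-8) and Table 3 (Cohort 9). Scans are every 8 weeks "until week 49 (~12 months) and then every 16 weeks" in Cohorts 1-8, and every 9 weeks "until week 49 (~12 months) and then every 18 weeks" in Cohort 9. Each scan has a window of 10 days either side, and all dates run from first dose.

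Protocol 9.4.4 states its gap rule as a scan count only, for patients in whom "two or more sequential assessments are missed, followed by the finding of tumor progression". It covers progression, not death. Protocol 9.4.3 has no gap rule for DOR.

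Separately, SAP 11.6.5 censors at Day 1 when "no disease assessments are performed during study treatment". Protocol 9.4.4 does so only for patients with no disease evaluation after first study treatment.

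**The concern.** A constant built for the 8- and 9-week schedule is applied unchanged after the interval doubles. From then on the day count and the words it is meant to explain describe different rules. Under the words, progression after one missed late scan is an event; under the day count it is censored. For deaths there is only the day count.

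The censoring is informative because the event triggers it. Take two patients who both miss one late scan. If the next scan shows stable disease, that patient stays at risk through that scan. If it shows progression, that patient is censored back at the previous evaluable scan and the event is lost. This pushes late PFS and DOR upward.

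The late part of these curves matters. Protocol 9.1 gives characterising the durability of disease control as one reason to expand a cohort to 40 patients. SAP 11.6.2 plans the median, the 25th percentile and the "75th percentile of DOR and their two-sided 95% CI", with Kaplan-Meier plots. Because wording and number disagree, two programmers could also produce different curves from the same data.

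The Day-1 wording has a related problem. Read literally, a patient who stops drug before the first scan and then progresses on the off-treatment scan that footnote 11 requires is censored at Day 1.

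**Working it through.** **Inputs.** Scan intervals, window and calendar anchor: SAP Tables 1 and 3, footnote 11. Thresholds of 122 and 136 days: SAP 11.6.5. Missed-scan rates and survival medians are not in the documents and are assumed below.

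**1. Reproduce the SAP's figures.** Threshold = 2 × interval + 10.
- Cohorts 1-8: 2 × 56 + 10 = 122.
- Cohort 9: 2 × 63 + 10 = 136.

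Both match, so on the early schedule the day count and the wording agree.

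**2. Apply the same constants after week 49.**

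| | Cohorts 1-8 | Cohort 9 |
|---|---|---|
| Late interval (days) | 16 × 7 = 112 | 18 × 7 = 126 |
| One interval + window | 112 + 10 = 122 | 126 + 10 = 136 |
| Two intervals + window | 2 × 112 + 10 = 234 | 2 × 126 + 10 = 262 |
| Progression at the next scan after one miss | 2 × 112 = 224 (204-244 with windows) | 2 × 126 = 252 (232-272 with windows) |

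The last row always exceeds 122 or 136.

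**3. The switch between schedules.** In Cohorts 1-8, with the last scan at week 40, week 48 missed and progression at week 64, the gap is (64 − 40) × 7 = 168 days. That is censored with one scan missed; two missed scans would need 56 + 112 + 10 = 178 days. In Cohort 9, assuming scans at weeks 36, 45 and 63, the gap is 27 × 7 = 189 days. Week 49 is not a multiple of 9 weeks (45, 54), so the documents do not fix where that switch falls.

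**4. No scan missed.** Progression on an exactly on-schedule late scan (112 or 126 days) is kept. Two in-window scans can be up to 132 or 146 days apart, so a scan that was not missed can reach the threshold. This needs a net drift of at least 10 days, and the day count must override the missed-or-non-evaluable wording.

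**5. Deaths.** On nominal dates, exactly one late scan has been missed between 112 and 224 days after the last evaluable scan (126 and 252 in Cohort 9).
- Cohorts 1-8: (224 − 122) / 112 = 102/112 = 91% of those days are dropped.
- Cohort 9: (252 − 136) / 126 = 116/126 = 92%.
- 8-week schedule: the one-miss range is 56-112 days, all below 122, so 0%.

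If a scan counts as missed only once its window has closed, one late scan is missed on days 122-233 (136-261 in Cohort 9), and every death in that range is dropped.

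**6. Share of late progressions affected.** Assume each scan is missed independently with probability m and there is no drift. Let a and b be the consecutive misses just before and just after progression. Each is geometric, so P(a + b = 1) = 2m(1 − m)².

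| m | Wrongly censored, 2m(1 − m)² | Two or more missed, correctly censored |
|---|---|---|
| 0 | 0% | 0% |
| 2% | 3.8% | 0.1% |
| 5% | 9.0% | 0.7% |
| 10% | 16.2% | 2.8% |

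**7. Effect on the planned statistics.** Simulation on the Cohorts 1-8 schedule: 60,000 patients per scenario, 48 months of follow-up, exponential medians of 5.6, 7.6 and 12 months, m = 5% or 10%, for PFS and DOR (12 scenarios). The day-count rule was compared with censoring only after two or more missed scans.
- Wrongly censored share of progressions found after week 48: 9-10% at m = 5% and 17-18% at m = 10%. This is slightly above step 6 because of the switch and truncation.
- Medians: unchanged in all 12 scenarios.
- 75th percentile: changed in one (PFS, 12-month median, m = 10%), from 25.8 to 29.5 months.

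**The case against.** For progression, the operative words in SAP 11.6.5 already require two missed scans and the day count is a parenthesis. A programmer who follows the words does no harm, so for progression this is an ambiguity rather than a wrong rule. That is fair as far as it goes. But the i.e. presents the day count as the definition, and the death rule has no wording to fall back on.

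The protocol also lets the SAP modify its plans (Section 9) and leaves time-to-event censoring to it (Section 9.2). So a departure from Protocol 9.4.4 is allowed. This is not a declared departure, however: the SAP still says two assessments and then gives a number that means one.

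The size is modest, and this stands. PFS and DOR are secondary and descriptive. The percentages in step 6 are shares of late progressions only; with a 5.6-month median and m = 5%, 2.6% of all patients are wrongly censored, about 1 in 40. The one percentile shift is a single step on the 16-week grid. It needs a 10% miss rate and a median PFS above the overall median survival the protocol quotes for nivolumab (8.74 months), pembrolizumab (10.1 and 11.3) and enfortumab monotherapy (11.7). The 91% and 92% are shares of days, and become shares of deaths only if deaths are spread evenly. Cohort 9 carries little weight, since SAP Figure 1 notes that its expansion will not open.

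A time cap has one real merit: dating progression at a scan 224 days after the last evaluable one also overstates PFS. The SAP does not give this as its reason, and a cap labelled as two missed scans is not a clear way to adopt it.

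On the Day-1 bullets, the SAP change history describes the rule as one for patients without an evaluation after first study treatment. This suggests that the protocol's meaning was intended, and the text should say so.

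**Conclusion.** The concern holds. The thresholds reproduce exactly as two early intervals plus the window, and equally exactly as one late interval plus the window. Followed as a day count, the plan censors all progressions found at the scheduled scan after a single missed late scan. It also drops deaths from day 122 (136 in Cohort 9) after the last evaluable scan, before two scans have been missed.

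Only patients still event-free at about 10 to 12 months or later are affected. The direction is upward, mainly in the tail of the PFS and DOR curves and occasionally at the 75th percentile. ORR is untouched, and medians reached before about 12 months barely move. The calendar arithmetic needs no outside figure. The size of the effect rests on assumed miss rates, independent misses, no drift and exponential event times. The correction should be made because the rule contradicts its own label and is cheap to repair.

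**What to change.** - In SAP 11.6.5, replace the 122/136-day counts for both progression and death. Censor only if two or more consecutive scheduled assessments between the last evaluable scan and the event were missed or non-evaluable.
- For deaths, count a scheduled assessment as missed only if its +10-day window closed before the death.
- List the nominal scan weeks, including where Cohort 9 moves to 18-weekly scans.
- In the Day-1 censoring bullets, replace the restriction to the study treatment period with *after first dose and before subsequent anti-cancer therapy*.
- If a cap on elapsed time is also wanted, state it as such and present it as a sensitivity analysis.

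The cost is SAP wording and programming, with no new data. Some late censorings become events, so the Kaplan-Meier tails will be slightly lower.
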